Peer Mentor Training & Monitoring The PI and study team will train Peer Mentors to deliver the intervention via 2 conveniently scheduled online training sessions each lasting approximately 2 hours, plus additional reading (about 40 minutes) and individual follow-ups with the Peer Mentor liaison as needed. Training will familiarize Peer Mentors with the intervention protocol and materials, introduce and role-play reflective listening skills and basic counseling techniques for interactions with participants, provide instruction and simulation of teaching strengths-based skills, emphasize the importance of helping young adults access their sources of social support, and clarify boundaries of their role as Peer Mentor (e.g., do not provide medical advice/answer medical questions, direct medical questions to diabetes care providers and mental health concerns directed to PI/social worker).

Peer Mentors will have monthly telephone-based individual and group supervision with the study team's Peer Mentor liaison for ongoing training and support and to ensure protocol fidelity. Peer Mentors will also be able to contact the Peer Mentor liaison and PI for any immediate concerns between supervisions. Intervention fidelity will be monitored in an ongoing manner: study staff/PI will review audio-recordings of each Peer Mentor's first session with each participant in comparison to a checklist of intervention components and delivery skills (e.g., asking open-ended questions, personalization). The Peer Mentor liaison will provide feedback based on the checklists, and if <75% of components are addressed adequately, additional training will be provided. The same process will be used to provide feedback and additional training based on Peer Mentors monthly self-assessments of topics addressed in the young adult-Peer Mentor contacts and the young adult-reports of Peer Mentor style and content at the 6-month time point (described below). As-needed booster training sessions for Peer Mentors (in person or via video-conference) will be conducted to maintain fidelity to the intervention protocol and prevent drift.

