INTERVENTION Condition After randomization, young adult participants in the intervention group will be assigned to a Peer Mentor. The study team Peer Mentor liaison will pair Peer Mentors with young adults taking into consideration gender, life circumstances (e.g., residential/schooling similarities), race/ethnicity, and availability. Each Peer Mentor will ideally be 1 year older than their assigned participant. Peer Mentors will be assigned 1-3 participants at a time, based on availability and performance. After being assigned, Peer Mentors will schedule a one-hour intervention session with their assigned participant at a convenient time within approximately 2 weeks of being paired together. This session may take place in person, by videoconferencing or telephone (while COVID-19 safety restrictions are in place, in-person meetings will not occur and we will not dictate what platform participants and Peer Mentors use.)

Following an intervention manual, the Peer Mentor will teach behavioral strategies and offer support to the young adult, including (a) teaching and modeling strengths-based skills for goal-setting, problem-solving, and stress management; (b) guiding participants in obtaining support from their social support network (e.g., family, friends); (c) developing a plan for accountability around diabetes management and follow-up in adult care; (d) sharing his/her transition experiences and strategies for

successfully navigating the adult healthcare system; (e) discussing how to prioritize diabetes self-care; and (f) assisting them in accessing diabetes-related resources (e.g., local diabetes groups, apps, social media).

During the first contact, the Peer Mentor will build rapport with the young adult (i.e., learn about his/her diabetes experiences and plans/expectations for the next year), guide them in setting diabetes and transition-related goals, and teach a strengths-based approach to recognizing and celebrating achievements toward those goals. The Peer Mentor will make frequent contact with the young adult via telephone, email, and/or text message (per young adult preference) to introduce the intervention content, help the young adult put it into practice, reinforce successes the young adult has in the transition process, and offer guidance and answer questions about following up in adult care.

(Continued in Section S- "Section F2 092121")

Section G: Sample Size/Data Analysis

G1. Sample Size

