How many subjects (or specimens, or charts) will be used in this study?

Local: 186 Worldwide: 186

Please indicate why you chose the sample size proposed:

We plan to enroll 150 young adult participants and up to 36 peer mentor participants (totaling 186 participants).

Sample Size and Power. A difference of 0.5 percentage points (e.g., reduction in HbA1c from 8.5% to 8.0%) is considered a clinically important difference in HbA1c. A sample size of 128 participants (64 per group) would be required to detect a 0.5 percentage point difference in mean HbA1c between treatment arms using an independent two-sample t-test assuming equal variances, common SD=1, and two-sided $\alpha=0.05$. Therefore, this study will plan to enroll and randomize 150 young adult participants (75/group) to allow for a conservative estimate of 15% attrition based on retention rates ranging between 86-96% in our previous intervention studies.

We will enroll up to 15 advisory board members. We are not collecting data from them so they are not included in sample size and power.

SUPPLEMENT ACTIVITIES SAMPLE SIZE: We plan to invite up to 35 young adult participants to complete the additional follow-up data collection. All participants for the Supplement Activities will be existing participants in the parent trial - there will be no new enrolled participants for the Supplement Activities.

G2. Data Analysis

Provide a description of your plan for data analysis. State the types of comparisons you plan (e.g. comparison of means, comparison of proportions, regressions, analysis of variance). Which is the PRIMARY comparison/analysis? How will the analyses proposed relate to the primary purposes of your study?

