Data Analysis Plan. Baseline demographics and clinical characteristics will be summarized by means with standard deviations, medians with minimum and maximum values, or frequencies with percentages. Summary statistics will be stratified by treatment arm and compared between groups using two-sample t-tests, Wilcoxon rank sum tests, or Fisher's exact tests. Approximate normality for continuous measures will be assessed using quantile-quantile plots and Shapiro-Wilks tests. Departures from normality will be addressed by data transformation (e.g., natural logarithm), categorization, or non-parametric analysis. Statistical significance for the univariable analysis will be assessed at the two-sided 0.05 level; however, significant differences between treatment arms must be due to chance since this is a randomized clinical trial. Missing data on questionnaires are expected to be minimal based on high follow-up data completion rates in preliminary intervention studies and <1% missing item responses in our preliminary study with a similarly-aged sample of young adults. Measures will be scored according to published instructions including rules for handling missing item responses. SAS v9.4 (Cary, NC) will be used for all data summaries and analysis. Aim 1: The primary outcome measure of interest is 12-month HbA1c. An independent, two-sample t-test will be used to compare mean HbA1c between study arms at the 12-month time point. An F test will be used to test the null hypothesis that the variances are equal, and approximate normality will be assessed using QQ-plots and the Shapiro Wilks test. Departures from model assumptions will be addressed by data transformations (e.g., natural logarithm), categorization, or alternative methods of analysis such as Welch's t-test approximation or the Wilcoxon rank sum test. Statistical significance will be assessed at the 0.05 level (2-sided). A general linear mixed model will be used to compare mean HbA1c between study arms after adjusting for baseline HbA1c and other clinically relevant covariates. Parameter estimates for the regression model will be assessed at the 0.05 level of significance (2-sided). Secondary outcomes include the time to first adult care visit, treatment adherence, and quality of life. The time to first adult care visit will be compared between treatment arms using the log-rank test statistic for comparing Kaplan-Meier curves. Time will start on the date of the last pediatric care visit. The event of interest is the date of the first adult care visit. Participants who do not follow-up with an adult care provider within 12 months of the last pediatric visit will be censored for the event at the 12-month time point. The log-rank test statistic will be assessed at the two-sided 0.05 level of significance. A Cox Proportional Hazards

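### Intervention participants share Peer Mentors, but G1 assumes independence and no between-arm analysis in G2 names a mentor term; one prespecified sensitivity analysis would cover this cheaply

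*Combined protocol and SAP*

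**What the plan says.** F2 (INTERVENTION Condition) gives a mentor to intervention participants only, after randomization. Pairing is deliberate rather than random: "The study team Peer Mentor liaison will pair Peer Mentors with young adults taking into consideration gender, life circumstances", and also race/ethnicity and availability. On workload, "Peer Mentors will be assigned 1-3 participants at a time, based on availability and performance". That limits the load at one moment, not the total over the trial. F2 continues in an attachment that is not in the text supplied and may say more about caseload.

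G1 states "We plan to enroll 150 young adult participants and up to 36 peer mentor participants", with 75 young adults per group. The sample size is derived "using an independent two-sample t-test assuming equal variances", a common SD of 1 and a two-sided 5% level. It gives no ICC or design effect.

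G2, Aim 1, states: "An independent, two-sample t-test will be used to compare mean HbA1c between study arms". A general linear mixed model will also "compare mean HbA1c between study arms after adjusting for baseline HbA1c and other clinically relevant covariates"; its random part is not described. Time to first adult visit is analysed by log-rank test and Cox model. For adherence and quality of life, only fixed effects are listed. Aim 3 concerns the mentors' own outcomes.

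**The concern.** Participants who share a mentor share part of their treatment. If some mentors are more effective than others, outcomes within a mentor's group are correlated, and the intervention mean varies more than 64 independent observations would suggest. Controls carry no such correlation, so the design is partially nested: clustered in one arm only.

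A t-test that ignores this uses a standard error that is too small for an effect meant to hold with other mentors. The alternatives listed in G2 (the variance F test, Welch, transformation, Wilcoxon) deal with unequal variance or shape, not dependence. At stake are the calibration of p-values and the width of confidence intervals for HbA1c and the secondary outcomes. The plan itself allows that mentors may perform differently, because it ties caseload to performance and provides retraining for those who miss intervention components.

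**Working it through.** **Inputs from the documents.** Difference 0.5 percentage points, SD 1, two-sided 5%, 64 analysed per arm, 75 randomised per arm, at most 36 mentors (all G1).

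**Assumption.** The documents give no ICC. The range 0.01 to 0.20 is assumed.

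**Reproducing the plan's figure.** For a two-sample t-test with difference 0.5 and SD 1, 80% power needs 63.8 per arm, so 64, as stated. G1 does not state its power; 80% is inferred, since 90% would need 85 per arm by the normal formula. At 64 per arm power is 80.1%. Allowing 15% attrition, 128/0.85 = 150.6, against 150 planned.

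**Sharing is unavoidable.** 75/36 = 2.08 participants per mentor at least, on average.

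**Formulas.** With m_j analysed participants for mentor j, the effective caseload is m = Σm_j²/64. The design effect in the intervention arm is DE = 1 + (m − 1) × ICC. The true standard error divided by the planned one is R = √[(1 + DE)/2], because only one arm is inflated. Type I error of the planned test is about 2[1 − Φ(1.96/R)]. Power of a correctly calibrated test uses variance (1 + DE)/64 and a noncentral t with 126 degrees of freedom.

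**36 mentors, loads as even as possible** (28 with two, 8 with one): m = (28×4 + 8×1)/64 = 1.875. At ICC 0.10, for example, DE = 1 + 0.875×0.10 = 1.0875, R = √(2.0875/2) = 1.0216, and type I error = 2[1 − Φ(1.96/1.0216)] = 5.5%.

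| Assumed ICC | DE | R | Type I error, planned t-test | Calibrated power |
|---|---|---|---|---|
| 0 | 1.0000 | 1.0000 | 5.00% | 80.1% |
| 0.01 | 1.0088 | 1.0022 | 5.05% | 80.0% |
| 0.05 | 1.0438 | 1.0109 | 5.25% | 79.3% |
| 0.10 | 1.0875 | 1.0216 | 5.51% | 78.4% |
| 0.20 | 1.1750 | 1.0428 | 6.02% | 76.8% |

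Simulation of the planned t-test agrees to about 0.1 percentage point. At a true difference of 0.5 it rejects in 79.8%, 79.6% and 79.1% of trials at ICC 0.05, 0.10 and 0.20. The rate barely falls because the test is slightly liberal.

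**Uneven loads.** With 22 mentors serving one participant and 14 serving three (illustrative), m = (22 + 14×9)/64 = 2.3125. At ICC 0.05/0.10/0.20, R = 1.016/1.032/1.064, simulated type I error is 5.4/5.8/6.6% and calibrated power is 78.9/77.6/75.1%.

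**Fewer mentors (assumed).** With 20 mentors (16 with three, 4 with four), m = (16×9 + 4×16)/64 = 3.25. At ICC 0.10, R = 1.055 and type I error is about 6.3%. With 11 mentors at ICC 0.10, simulation gives about 7.9%. Cumulative caseload is not capped in the supplied text, so none of these is a bound.

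**Better retention.** G1 calls its figure a "conservative estimate of 15% attrition based on retention rates ranging between 86-96% in our previous intervention studies". At 96%, 75 × 0.96 = 72 per arm (two per mentor, m = 2), and calibrated power is 84.6% at ICC 0 and 81.1% at ICC 0.20.

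**A different target.** If mentor effects are constrained to average zero over the participants served, so that inference is about these mentors only, the planned t-test rejects in about 4.7/4.4/3.9% of simulated null trials at ICC 0.05/0.10/0.20. It is then slightly conservative.

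**The case against.** The strongest reply is that the inflation depends on a choice the plan has not made. It needs an average effect of zero, real differences between mentors, and a conclusion meant for mentors other than those who served. If the programme affects nobody, or if the question concerns only the mentors who took part, the planned test is not liberal. This stands, and the sensitivity analysis should therefore state its target.

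The plan also works to keep mentor differences small, through a manual, monthly supervision, retraining, and staff comparison of each mentor's "first session with each participant in comparison to a checklist of intervention components and delivery skills". A low ICC is plausible, and at 0.01 the effect is negligible. This stands too, although the documents give no figure to settle it.

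The adjusted HbA1c model is called a mixed model, so a mentor effect may have been intended. It is fair to say that the term is unstated rather than ruled out.

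Finally, a nested model will estimate mentor variance poorly, and non-random matching mixes case mix with mentor effect. Both are true. They are reasons to place the analysis beside the planned tests, not in their stead.

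A reader might infer that the primary t-test is invalid or that the trial is too small. The documents do not support either: at up to 36 mentors the calibrated loss is a few power points even at ICC 0.20, and the retention range in G1 leaves room to absorb it.

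**Conclusion.** The point holds as a cheap improvement of low severity. Sharing of mentors follows from the plan's own numbers, G1 assumes independence, and no between-arm analysis in G2 accounts for mentor.

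With 36 evenly loaded mentors and ICC 0.01 to 0.20, the true standard error of the arm difference is 0.2% to 4.3% above the planned one, and type I error is about 5.1% to 6.0%. The effect grows if fewer mentors serve. These figures rest on an assumed ICC, 64 analysed per arm, equal total variance in both arms, and generalisation beyond the mentors who served. Without that last condition, or if the programme affects nobody, there is no inflation. The primary conclusion is not threatened and the sample size need not change.

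**What to change.** Keep mentor ID in the analysis dataset and add to G2, beside the planned tests:

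- **12-month HbA1c:** one named sensitivity analysis by a partially nested mixed model, with a mentor random effect in the intervention arm only, arm-specific residual variance, and Satterthwaite or Kenward-Roger degrees of freedom. Adjust for baseline HbA1c and only those matching characteristics recorded in both arms, such as gender and race/ethnicity. Availability, for instance, is not shown to be recorded for controls.
- **Adherence and quality of life:** the same mentor term added to the planned models.
- **Time to first adult visit:** mentor-clustered robust variance in the Cox model, each control being its own cluster. This also serves as the sensitivity check for the log-rank test.
- **Interpretation:** state that the analysis targets generalisation over mentors, and that if mentor variance is estimated as zero, the model without it is reported.

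The cost is SAP wording and one variable. The liaison makes the pairings and staff review each first session, so the link is already known.

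There are three statistical downsides, from simulations of a continuous outcome with variance components and Satterthwaite degrees of freedom:

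- **Slightly wider intervals.** Power of the nested analysis with 36 evenly loaded mentors is 79.0% at ICC 0 and 77.6% at ICC 0.10; with 20 mentors it is 78.1% and 74.5%.
- **Imprecise mentor variance.** It is estimated as zero in 49% of trials at ICC 0 and 30% at ICC 0.10.
- **Some conservatism from matching.** If pairing sorts participants completely on an unadjusted covariate explaining 10% or 30% of variance, and mentors have no effect, the t-test holds 5.0% while the nested analysis falls to 4.4% or 3.6% type I error, with 78.2% or 76.1% power.

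Kenward-Roger degrees of freedom and the clustered Cox variance were not simulated.

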We will be collaborating with the BCM Young Adult Diabetes Clinic, which is led by [name] who is a collaborator on this protocol. The Young Adult clinic will assist in the recruitment of Peer Mentors by posting the attached flyer (Section R) in their clinic, discussing the study with clinic patients both in person and by email, and sharing with the study team phone numbers/contact information for young adult patients who have expressed to [name] (or her affiliates at the clinic) an interest in learning more about becoming a Peer Mentor (and have verbally agreed to have their contact information shared for this purpose). Staff at the BCM Young Adult clinic will also notify study staff when they receive a referral for transfer of care from TCH Diabetes Care Center through the TCH electronic medical record (EPIC), to facilitate potential recruitment for the study.

Additionally, we will obtain releases of information to request medical chart data about study participants from any adult care providers they see for diabetes care during their time in our study, as detailed below. To protect confidentiality, all patient information the BCM Young Adult Clinic shares with our study team will be via secure email, BCM's Microsoft OneDrive, or via EPIC InBasket.

Will you obtain a Certificate of Confidentiality (COC) for this study?

Yes

Please further discuss any potential confidentiality issues related to this study.

We will obtain releases of information to request medical and appointment data from adult care providers. We will ask participants, at enrollment, to provide the names and contact information for family or friends who may help us locate the participants at follow-up if we are unable to make contact then.

Will information about the subject's participation be included in subject's medical records?

Yes

Please further discuss any potential confidentiality issues related to this study.

Participation is recorded in EPIC research tab

Section L: Cost/Payment

Delineate clinical procedures from research procedures. Will subject's insurance (or subject) be responsible for research related costs? If so state for which items subject's insurance (or subject) will be responsible (surgery, device, drugs, etc). If appropriate, discuss the availability of financial counseling.

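### The test stated for the primary outcome is an unadjusted comparison of participants with a 12-month HbA1c; it is biased if loss differs by arm, and the baseline-adjusted model already planned should be primary, backed by a sensitivity analysis

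*Combined protocol and SAP*

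**What the plan says.** Section G2, Aim 1, names the endpoint ("The primary outcome measure of interest is 12-month HbA1c") and the test: "An independent, two-sample t-test will be used to compare mean HbA1c between study arms at the 12-month time point". The sample size in Section G1 is built on the same t-test. It needs 128 evaluable participants and randomizes 150, "to allow for a conservative estimate of 15% attrition based on retention rates ranging between 86-96% in our previous intervention studies".

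Directly after the t-test, Aim 1 adds a general linear mixed model for HbA1c, adjusted for baseline HbA1c and for further clinically relevant covariates that are not named. The plan does not call this model primary.

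The missing-data text in Section G2 concerns questionnaires: "Missing data on questionnaires are expected to be minimal", followed by scoring rules for missing items. The text supplied gives no analysis population, no method for a missing 12-month HbA1c, no assumption about why values are missing, and no sensitivity analysis for them.

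HbA1c kits are mailed at baseline and 12 months only (Section N). Section K adds that "we will obtain releases of information to request medical chart data about study participants from any adult care providers" seen for diabetes during the study, but does not say that a chart value would replace a missing study value.

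**The concern.** A t-test of 12-month values drops everyone without one. The 15% allowance restores power for that loss; it does nothing for validity.

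Reassurance about questionnaires does not carry over to HbA1c. The home sample is a separate task: a deeper finger poke, three filled circles, three hours of drying and a return mailing (Section F2). It is also paid separately, $25 against $75 for the 12-month questionnaires (Section L). A participant can complete one and not the other.

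The arms also differ in ways that could affect who remains. One arm has frequent mentor contact and an accountability plan for a year; the other has usual care. If retention, or the kind of participant retained, differs as a result, the comparison of those observed departs from the comparison of those randomized. At stake is a distortion of the primary estimate that the stated test cannot reveal.

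**Working it through.** **Inputs from the documents.** Target difference 0.5 points, SD 1, two-sided 0.05, 64 per arm evaluable, 75 per arm randomized, 15% attrition (Section G1); HbA1c at baseline and 12 months only (Section N). Power is not stated; 80% is assumed because it reproduces the plan's figure.

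**The plan's own figure.** The exact t-test calculation gives 63.77, so 64 per arm (128 in total) with power 80.1%. Then 128/0.85 = 150.6, and 150 × 0.85 = 127.5 expected completers. The plan's 128 and 150 are reproduced. The expected loss is 150 × 0.15 = 22.5 people.

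**Bias formula.** In an arm, let d be the share lost and g the mean HbA1c of those lost minus that of completers. The completers' mean is the full-arm mean minus d × g. Hence

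bias (intervention minus control) = d₀g₀ − d₁g₁.

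This is zero when both arms lose the same share with the same gap, whatever the share. With no true effect and SD 1:

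| Loss, one arm / other | Gap g | Absolute bias | Type I error |
|---|---|---|---|
| 15% / 15% | 1.0 in both | 0.15 − 0.15 = 0 | 5.0% |
| 12% / 18% | 1.0 in both | 0.18 − 0.12 = 0.06 | 6.3% |
| 10% / 20% | 1.0 in both | 0.20 − 0.10 = 0.10 | 8.7% |
| 15% / 15% | 1.0 in one arm, 0 in the other | 0.15 × 1.0 = 0.15 | 13.4% |

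**Simulation.** No true effect, SD 1, 75 per arm, assumed baseline to 12-month correlation 0.6, 20,000 trials per row. Where loss is related to HbA1c, it is logistic with log-odds of 1 per SD in absolute size. The adjusted analysis is a regression of the observed 12-month values on arm and baseline.

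| Loss depends on | Pattern | t-test: bias, type I error | Baseline-adjusted: bias, type I error |
|---|---|---|---|
| Baseline | 15% each, same relation | 0.00, 5.0% | 0.00, 5.1% |
| Baseline | 15% each, related in one arm only | 0.08, 7.3% | 0.00, 5.0% |
| Baseline | 15% each, opposite directions | 0.16, 14.9% | 0.00, 5.2% |
| 12-month value | 10% vs 20%, same relation | 0.084, 7.8% | 0.056, 6.8% |
| 12-month value | 15% each, related in one arm only | 0.131, 11.9% | 0.085, 9.4% |

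Varying the correlation from 0.5 to 0.7 (6,000 trials each) moves the one-arm, baseline-related row to a bias of 0.067 to 0.096 and type I error of 6.6 to 8.0%. That is 0.067/0.5 = 13% to 0.096/0.5 = 19% of the target difference. The sign depends on which arm loses the participants.

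**Precision.** The unadjusted standard error is √(2/63.75) = 0.177. Adjustment multiplies it by √(1 − r²): 0.177 × √0.75 = 0.153 at r = 0.5, and 0.177 × √0.51 = 0.126 at r = 0.7.

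**What the planned model does with the missing.** With baseline as a covariate and one later HbA1c value, each person contributes a single outcome. Anyone without a 12-month value therefore drops out of the mixed model too.

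**The case against.** The strongest reply is that the plan already contains the correction. A reader might infer from the t-test that baseline HbA1c goes unused and that nothing would expose a problem. The documents do not support that: the adjusted model stands right after the t-test, and a gap between the two results would be a warning. In every scenario where loss depends on baseline alone, that model restores a bias of about zero and type I error of about 5%. This stands in full. What it leaves open is which result decides the trial, and loss for reasons that baseline does not capture.

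Second, a reader might infer that 15% attrition by itself biases the test. It does not; the amount of loss or its relation to HbA1c must differ by arm, and the documents neither show nor exclude this. Loss in opposite directions is a stress case with no support in the text. Retention measures cover both arms: back-up contacts and social media (Section F2) and rising payments (Section L). Past retention of 86 to 96% implies 4 to 14% lost. Rerunning the one-arm, baseline-related scenario at 9% loss gives a bias of 0.04 to 0.06 and type I error of about 6%; at 4% loss, 0.02 to 0.03 and 5.0 to 5.7%. The size claimed here therefore belongs to the plan's own planning figure and shrinks with better retention.

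Third, it is not established that only a returned kit can count at 12 months. Section F2 accepts a recent clinic or laboratory value at baseline, and that section continues in an attachment outside the text supplied. So the point concerns participants without any 12-month value. Section G2 is not marked as continued elsewhere.

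**Conclusion.** The concern holds in a limited form. The test stated for the primary outcome compares only participants with a 12-month HbA1c, without adjustment, and is open to bias if loss works differently in the two arms. At the plan's own 15%, with loss related to baseline HbA1c in one arm only, the bias is about 0.07 to 0.10 points and type I error about 7 to 8%. That rests on an assumed log-odds of 1 per SD and a correlation of 0.5 to 0.7. With the same mechanism in both arms, the bias is zero.

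The planned baseline-adjusted model removes that bias and is more precise, but it is not the designated primary analysis. It only reduces bias from loss tied to the 12-month value itself (0.084 to 0.056 in the 10% versus 20% case), so a sensitivity analysis is still needed. The documents do not support the stronger reading that the primary result will be biased. The sample size is sound and does not change.

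**What to change.** In Section G2, Aim 1:

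- Make the comparison adjusted for baseline HbA1c, by arm assigned, the primary analysis. Keep the unadjusted t-test as supportive.
- Include all randomized participants through multiple imputation of missing 12-month HbA1c within arm, using baseline HbA1c and the 6-month measures. The 6-month measures carry the gain here, since the adjusted model already uses baseline.
- Add a delta-adjusted (tipping-point) analysis. With 15% missing in an arm, shifting its imputed values by δ moves the arm difference by 0.15 × δ, so δ = 1.0 moves it by 0.15 points.
- Report 12-month HbA1c availability by arm.
- Use adult-care chart HbA1c only in a sensitivity analysis. Its availability may depend on arm, because time to first adult visit is an outcome the intervention targets (Section D).

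The cost is plan wording and a few hours of programming in the SAS release already named, with no new visits, kits or participants. The downside is reliance on a missing-at-random assumption, which the tipping-point analysis examines. The change should be fixed before outcome data by arm are seen.
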